Serial 7 subtraction starting at 100. [] 93 [] 86 [] 79 [] 72 [] 65 4 or 5 correct subtractions: 3 pts, 2 or 3 correct: 2 pts, 1 correct: 1 pt, 0 correct: 0 pt				—/3
LANGUAGE Repeat: I only know that John is the one to help today. The cat always hid under the couch when dogs were in the room.				—/2
Fluency / Name maximum number of words in one minute that begin with the letter F.		[] _____ (N=11 words)		—/1
ABSTRACTION Similarity between e.g. banana - orange = fruit		[] train - bicycle  [] watch - ruler 		—/2
DELAYED RECALL (MIS)		Has to recall words WITH NO CUE  X3  X2  X1 		Points for UNCLUED recall only MIS = _____/15
Memory Index Score (MIS)		FACE  VELVET  CHURCH  DAISY  RED 		
ORIENTATION		[] Date  [] Month  [] Year  [] Day  [] Place  [] City 		
© Z. Nasreddine MD Administered by: _____ Training and Certification are required to ensure accuracy		MIS:  15 (Normal ≥ 26/30) Add 1 point if ≤ 12 yr edu		TOTAL  30

AMC Linear Disability Score (ALDS)

Introduction

Assessing the clinically meaningful effect on outcome in stroke patients allows more accurate interpretation in clinical trials. The AMC (Academic Medical Center) Linear Disability Score (ALDS) is a calibrated generic item bank to measure the level of physical disability in patients. The ALDS is a sensitive and generic disability scale which measures a broader range of activities compare to the Rankin assessment. The major difference between the ALDS and the Rankin assessment is that the ALDS is a linear disability score assessment and is a patient-reported outcome whereas the Rankin score is an ordinal disability score assessment and is a rater-assigned outcome.

General Instructions

Sources of Information

Obtain information from the same people that provided answers for the Rankin Focused Assessment (RFA).

Choose the Right Assessment

This assessment is intended for use after completing the Rankin Focused Assessment (RFA). There are different sets of questions matched to each Rankin score result. Choose the AMC Linear Disability Score (ALDS) question set according to the Rankin score. For example, if your patient has Rankin score of 3, then assess ALDS 3 question set. However, if every question in the initial ALDS question set ends up marked 'Yes' or 'NA', then please proceed to next lower numbered ALDS question set and complete the assessment *unique* to that ALDS set. For example, if your patient has a Rankin score of 2, then assess ALDS 2. However, if the patient answered all the questions in ALDS 2 'Yes' or 'NA' then proceed to ALDS 1 and assess all the *unique* questions in ALDS 1 that were not in ALDS 2. Similarly, if every question in the initial ALDS question set ends up marked 'No' or 'NA', then please proceed to next higher numbered ALDS question set and complete the assessment *unique* to that ALDS set. For example, if your patient has a Rankin score of 2, then you will complete ALDS 2. If the patient answered all the questions in ALDS 2 'No' or 'NA' then proceed to ALDS 3 and complete all the *unique* questions in ALDS 3.

Rankin Score	Assessment
Rankin Score 0	ALDS 1
Rankin Score 1	ALDS 1
Rankin Score 2	ALDS 2
Rankin Score 3	ALDS 3
Rankin Score 4	ALDS 4
Rankin Score 5	ALDS 5

Scoring Instructions

There are two response options which are 'Yes' and 'No'. If a patient responds that he/she can carry out the activity but only with difficulty, then 'Yes' should be marked. If a patient says the question is not applicable because the patient has never attempted the activity in the question after stroke, then mark the 'NA' box. The answer should reflect what the patient can do without assistance of another person. However, assistance of a walker, cane and other prosthetic devices are fine.

Visit Nurse Name : _____

Patient Number : _____ Subject Initials : _____ Date of Visit : ___ / ___ / ___

AMC Linear Disability Score Rating Form

Information for completing this form was obtained from (please check all that apply) :

 Patient	 Sister
 Spouse	 Brother
 Son	 Other relative, specify relationship : _____
 Daughter	 Friend
 Father	 Nurse
 Mother	 Home health aide
 Physical therapist	 Occupational therapist
 Speech therapist	 Physician
 Other individual, specify role: _____	

Please mark (X) in the appropriate box. Choose the questionnaire according to the Rankin Score. Please assess all the questions. See the instruction sheets for further information.

ALDS 1 : Assessment for Patient with Rankin Score 0 or Rankin Score 1			
		Yes	No
1	Can you vacuum a flight of stairs?		
2	Can you carry a bag of shopping upstairs?		
3	Can you go for a walk in the woods?		
4	Can you travel by local bus?		
5	Can you carry a tray?		
6	Can you walk up a hill?		
7	Can you cut your toe nails?		
8	Can you stand for 10 minutes?		
9	Can you use a washing machine?		
10	Can you walk down a flight of stairs?		
11	Can you go for a short walk (15 min)?		
12	Can you change the sheets on a bed?		
13	Can you buy a few things from the store?		
14	Can you take a shower and wash your hair?		
15	Can you pick something up from the floor?		

Visit Nurse Name : _____

Patient Number : _____ Subject Initials : _____ Date of Visit : ___ / ___ / ___

Please mark (X) in the appropriate box. Choose the questionnaire according to the Rankin Score. Please assess all the questions. See the instruction sheets for further information.

ALDS 2 : Assessment for Patient with Rankin Score 2

		Yes	No	NA
1	Can you vacuum a flight of stairs?			
2	Can you carry a bag of shopping upstairs?			
3	Can you go for a walk in the woods?			
4	Can you travel by local bus?			
5	Can you carry a tray?			
6	Can you go shopping for clothes?			
7	Can you cut your toe nails?			
8	Can you stand for 10 minutes?			
9	Can you use a washing machine?			
10	Can you walk down a flight of stairs?			
11	Can you change the sheets on a bed?			
12	Can you buy a few things from the store?			
13	Can you take a shower and wash your hair?			
14	Can you pick something up from the floor?			
15	Can you prepare breakfast or lunch?			

ALDS 3 : Assessment for Patient with Rankin Score 3

		Yes	No	NA
1	Can you travel by local bus?			
2	Can you carry a tray?			
3	Can you cut your toe nails?			
4	Can you stand for 10 minutes?			
5	Can you walk down a flight of stairs?			
6	Can you go for a short walk (15 min)?			
7	Can you change the sheets on a bed?			
8	Can you take a shower and wash your hair?			
9	Can you pick something up from the floor?			
10	Can you get in and out of a car?			
11	Can you prepare breakfast or lunch?			
12	Can you put on/take off socks and slippers?			
13	Can you sit on the edge of a bed from lying down?			
14	Can you put on and take off a coat?			
15	Can you walk to and get on and off the toilet?			

Visit Nurse Name : _____

Patient Number : _____ Subject Initials : _____ Date of Visit : ___ / ___ / ___

Please mark (X) in the appropriate box. Choose the questionnaire according to the Rankin Score. Please assess all the questions. See the instruction sheets for further information.

ALDS 4 : Assessment for Patient with Rankin Score 4

	Yes	No	NA
1 Can you carry a tray?			
2 Can you walk up a flight of stairs?			
3 Can you buy a few things from the store?			
4 Can you take a shower and wash your hair?			
5 Can you pick something up from the floor?			
6 Can you get in and out of a car?			
7 Can you peel and core an apple?			
8 Can you prepare breakfast or lunch?			
9 Can you eat a meal at the table?			
10 Can you put on/take off socks and slippers?			
11 Can you put pants on?			
12 Can you sit on the edge of a bed from lying down?			
13 Can you put on and take off a coat?			
14 Can you walk to and get on and off the toilet?			
15 Can you wash your lower body when taken to sink?			

ALDS 5 : Assessment for Patient with Rankin Score 5

	Yes	No	NA
1 Can you change the sheets on a bed?			
2 Can you pick something up from the floor?			
3 Can you get in and out of a car?			
4 Can you peel and core an apple?			
5 Can you eat a meal at the table?			
6 Can you put on/take off socks and slippers?			
7 Can you sit up (from lying) in bed?			
8 Can you get a book off the shelf?			
9 Can you answer the telephone?			
10 Can you make a bowl of cereal?			
11 Can you move between two dining chairs?			
12 Can you wash and dry your lower body?			
13 Can you put on and take off a coat?			
14 Can you wash and dry your face and hands?			
15 Can you get out of bed into a chair?			

**PATIENT HEALTH QUESTIONNAIRE-8
(PHQ-8)**

Over the last 2 weeks, how often have you been bothered by any of the following problems?
(Use "✓" to indicate your answer)

	Not at all	Several days	More than half the days	Nearly every day
1. Little interest or pleasure in doing things	0	1	2	3
2. Feeling down, depressed, or hopeless	0	1	2	3
3. Trouble falling or staying asleep, or sleeping too much	0	1	2	3
4. Feeling tired or having little energy	0	1	2	3
5. Poor appetite or overeating	0	1	2	3
6. Feeling bad about yourself — or that you are a failure or have let yourself or your family down	0	1	2	3
7. Trouble concentrating on things, such as reading the newspaper or watching television	0	1	2	3
8. Moving or speaking so slowly that other people could have noticed. Or the opposite — being so fidgety or restless that you have been moving around a lot more than usual	0	1	2	3

If you checked off any problems, how difficult have these problems made it for you to do your work, take care of things at home, or get along with other people?

Not difficult at all	Somewhat difficult	Very difficult	Extremely difficult
			

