12 APPENDICES

12.1 APPENDIX 1 – QUESTIONNAIRES AND FUNCTIONAL TEST

Study Number: _____ Subject Initials: _____ Date of Visit: ____ / ____ / ____

Rating Form

Rankin Focused Assessment - Ambulation (RFA-A)

Name of rater performing assessment: _____

Information for completing this form was obtained from (check all that apply):

 Patient  Spouse  Son  Daughter  Father  Mother  Physical therapist  Speech therapist  Medical record  Other individual, specify role: _____	 Sister  Brother  Other relative, specify relationship: _____  Friend  Nurse  Home health aide  Occupational therapist  Physician
---	--

Please mark (X) in the appropriate box. Please record responses to all questions (unless otherwise indicated in the text). Please see instruction sheets for further information.

5 BEDRIDDEN**5.1 Is the person bedridden?**

The patient is unable to walk even with another person's assistance. May frequently be incontinent. May require constant care

Yes No
(5)

If yes, explain:

4 ASSISTANCE TO WALK**4.1 Is another person's assistance essential for walking?**

Requiring another person's assistance means needing another person to be always present when walking, including indoors around house or ward, to provide physical help, verbal instruction, or supervision.

(Patients who use physical aids to walk, e.g. stick/cane, walking frame/walker, but do not require another person's help, are NOT rated as requiring assistance to walk).

Yes No
(4)

If yes, explain:

Study Number: _____ Subject Initials: _____ Date of Visit: ____ / ____ / ____

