- (F) Count the number of blocks transported and record. Subtract blocks transported more than one at a time or if the fingertips did not cross over. Return all blocks to one side of the divider.*
- Move the box so that all the blocks are on the same side as the next hand to be tested.
- "Now you are to do the same thing with your (left/right) hand.*
- REPEAT (A) - (F) with the left/right hand*

SCORING BOX

Score for Right Hand	Score for Left Hand	Affected hand was (circle one)
		Right Left

10-Meter Walk Test: Instructions and Scoring Sheet

Description: The 10-Meter Walk Test is a measure of gait speed

Equipment Needed:

- 2 chairs
- digital stopwatch with hundredths of a second resolution
- measuring tape
- bright-colored masking tape
- open hallway or space

Set-Up Of The Course:

- Find a long hallway or other open space that is free from distractions or traffic
- The course should be straight, level, and flat, with no turns or corners
- The total length of the course is 14 meters
- Use bright-colored masking tape to mark four lines on the course at 0, 2, 12 and 14 meters, as per below (do not place tape along the dashed line):

Subjects:

- Wear normal supportive foot apparel. If slippers are worn, they must be well-fitting and not floppy
- Wear any orthotics that are normally worn (e.g. AFO etc.)
- Use any assistive device that are normally used for balance and/or stability (e.g. cane or walker)

What Physical Assistance Is Allowed:

- ALLOWED: Physical assistance with ambulation from one person, such as a therapist
- ALLOWED: A therapist may walk aside or behind the subject to provide assistance for safety
- NOT ALLOWED: Physical assistance with ambulation from two or more persons. If this is needed, the subject is considered non-ambulatory, is not tested, and maximum score (300 seconds) is entered
- NOT ALLOWED: The therapist may not advance the subject's leg. If a subject cannot advance his/her own leg, he/she is considered non-ambulatory, is not tested, and maximum score (300 seconds) is entered
- If the patient requires 2 or more persons, or help advancing the leg, do not test gait

Test Administration:

- Show the subjects the start and stop points
- Seat the subject in the 0-meter chair during instructions
- When ready to begin testing, **the subject starts in a standing position at the 0-meter line**
- Instruct the subject to walk to the 14-meter chair after you give the “Ready and Go” signal

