- **NOT ALLOWED:** Talking during walking. Neither the examiner nor subject should talk during testing
- **NOT ALLOWED:** Encouragement during walking. **During walking, do not encourage the subject in anyway.**
- Do not mention the tape locations on the floor—only the location of the 14-meter chair
- **At all times, patient safety is number one.** If you cannot test gait safely using above rules, do not score the 10-meter walk test.

Verbal Directives:

- **WHEN THE SUBJECT IS SEATED**, say: “You are going to walk to the far chair, which is a distance of 10 meters, or just over 30 feet. You should walk at your usual or normal pace. Do you have any questions?” Subjects should not run to achieve a good score, rather, subjects should walk at their usual or normal pace.
- **WHEN THE SUBJECT IS STANDING AT THE 0-METER MARK** and is ready to start, say: “Remember, you are to walk to the far chair at your usual or normal pace once I say the start command of ‘Ready and Go’”
- **CONFIRM THE SUBJECT IS READY AND THEN SAY “Ready and Go”**

Recording Time: First Trial

- After you say “Ready and Go”:
- **START THE STOPWATCH** the moment that any part of the subject’s foot first crosses the 2-meter line
- **STOP THE STOPWATCH** the moment any part of the subject’s foot crosses the 12-meter line
- **RECORD THE TIME IN SECONDS** (using hundredths of a second resolution). This is the time in seconds that it took for the subject to travel between the 2-meter and the 12-meter lines

Recording the Time: Second Trial

- **ALLOW a 2 minute rest in the 14-meter chair before starting the second trial**
- **The subject starts in a standing position at the 14-meter line**
- Start the stopwatch the moment that any part the subject’s foot crosses the 12-meter line and stop the stopwatch at the moment that any part of the subject’s foot crosses the 2-meter line
- Record the time in seconds (at hundredths of a second resolution) it took the subject to

travel from the 12-meter line to the 2-meter line

Recording Outcomes:

- Record values from both trials into the database
- If the subject cannot take even one step, record the time as maximum time (300 seconds)
- If the subject takes longer than 5 minutes (300 seconds) to complete the test, stop testing at 5 minutes and record a time of 300 seconds
- If an attempt cannot be made to evaluate gait velocity testing, then enter a score of 9999 in both boxes for # seconds and record reason for not testing

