- Remember, it is critical to distinguish subjects who are assessed and are very slow or unable to walk (enter 300 seconds) from subjects who cannot be tested (enter 9999)

seconds on Trial 1 _____

seconds on Trial 2 _____

If an attempt cannot be made to evaluate gait velocity, please provide explanation here:

If an assistive or orthotic device was used, please record the type here:

Stroke Impact Scale

VERSION 3.0

The purpose of this questionnaire is to evaluate how stroke has impacted your health and life. We want to know from **YOUR POINT OF VIEW** how stroke has affected you. We will ask you questions about impairments and disabilities caused by your stroke, as well as how stroke has affected your quality of life. Finally, we will ask you to rate how much you think you have recovered from your stroke.

**The following questions are about your ability to use your hand that was
MOST AFFECTED by your stroke.**

7. In the past 1-2 days, how difficult was it to use your hand that was most affected by your stroke to...	Not difficult at all	A little difficult	Somewhat difficult	Very difficult	Could not do at all
a. Carry heavy objects (e.g. bag of groceries)?	5	4	3	2	1
b. Turn a doorknob?	5	4	3	2	1
c. Open a can or jar?	5	4	3	2	1
d. Tie a shoe lace?	5	4	3	2	1
e. Pick up a dime?	5	4	3	2	1

Stroke Impact Scale

VERSION 3.0

The purpose of this questionnaire is to evaluate how stroke has impacted your health and life. We want to know from **YOUR POINT OF VIEW** how stroke has affected you. We will ask you questions about impairments and disabilities caused by your stroke, as well as how stroke has affected your quality of life. Finally, we will ask you to rate how much you think you have recovered from your stroke.

The following questions are about your ability to use your hand that was MOST AFFECTED by your stroke.

7. In the past 2 weeks, how difficult was it to use your hand that was most affected by your stroke to...	Not difficult at all	A little difficult	Somewhat difficult	Very difficult	Could not do at all
a. Carry heavy objects (e.g. bag of groceries)?	5	4	3	2	1
b. Turn a doorknob?	5	4	3	2	1
c. Open a can or jar?	5	4	3	2	1
d. Tie a shoe lace?	5	4	3	2	1
e. Pick up a dime?	5	4	3	2	1

STROKE IMPACT SCALE 16 (SIS-16)

1. Explain to the subject what the questionnaire is about: "Now I am going to ask some questions about how much difficulty you have had while performing some activities in the past 1-2 days"

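### The 10-Meter Walk Test form gives conflicting entries (300 seconds or no usable value) for a patient not walked because of gait impairment, so the rater's choice of line decides whether that patient counts in the third secondary endpoint

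*Protocol*

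**What the plan says.** The instructions are on the 10-Meter Walk Test sheet in Protocol Appendix 1 (Section 12.1), under three subheadings.

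- **What Physical Assistance Is Allowed.** Help from one person is permitted. For a subject who needs two or more: "If this is needed, the subject is considered non-ambulatory, is not tested, and maximum score (300 seconds) is entered". For a subject who cannot advance the leg: "he/she is considered non-ambulatory, is not tested, and maximum score (300 seconds) is entered".
- **Test Administration.** "If you cannot test gait safely using above rules, do not score the 10-meter walk test".
- **Recording Outcomes.** "If the subject cannot take even one step, record the time as maximum time (300 seconds"). If no attempt can be made, the rater must "then enter a score of 9999 in both boxes for # seconds and record reason for not testing". The closing reminder calls it critical to separate "subjects who are assessed and are very slow or unable to walk (enter 300 seconds") "from subjects who cannot be tested (enter 9999").

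Sections 3 and 9.4.1 make gait speed on this test, as change from baseline to Day 90, the third secondary endpoint in a fixed sequence. Section 9.4.3 compares it between groups by analysis of variance adjusted for baseline where relevant. Section 5.1 enrols mRS 3 or 4 at 4 to 21 days after stroke. On the trial's mRS rating form, grade 4 turns on needing help to walk: "Requiring another person's assistance means needing another person to be always present when walking".

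**The concern.** A floor value and a missing value are very different data. The form separates them by two criteria that disagree. In the assistance rules, 300 seconds is the entry for a subject who is not tested. In the closing reminder, 300 seconds belongs to subjects who are assessed, and untested subjects get 9999. Between the two stands an instruction not to score at all.

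A change from baseline needs a number at both visits. A patient unscored or coded 9999 at baseline has no observed change, even if walking by Day 90. A patient who walked at baseline but is left unscored at Day 90 for gait reasons is lost because the outcome was bad. The endpoint is the only performance-based lower-limb measure behind the secondary objective, and endpoints 4 to 6 can be claimed only if it succeeds.

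**Working it through.** **1. The rules side by side**

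| Place on the form | Situation | Entry |
|---|---|---|
| Assistance rules | Needs two or more persons; not tested | 300 s |
| Assistance rules | Cannot advance own leg; not tested | 300 s |
| Test Administration | Cannot be tested safely under the rules above it | no score |
| Recording Outcomes | Cannot take one step | 300 s |
| Recording Outcomes | Over 5 minutes | 300 s |
| Recording Outcomes | No attempt can be made | 9999, with reason |
| Closing reminder | Assessed, very slow or unable to walk | 300 s |
| Closing reminder | Cannot be tested | 9999 |

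**2. Three patients run through the rules**

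- *Needs two helpers.* The assistance rules give 300 s. The patient also cannot be tested safely within the one-person limit, so Test Administration says no score. No attempt is made, so Recording Outcomes and the reminder point to 9999.
- *Cannot take a step.* 300 s if the rater counts this as assessed; 9999 if the rater judges that no attempt can be made.
- *One helper available, leg advances, but the therapist judges the walk unsafe.* No 300 s trigger fits literally. Test Administration gives no score, although the reason is gait impairment.

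No score and 9999 both leave no usable value. The effective choice is an analysed 300 s or missing.

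**3. What the choice is worth for one patient**

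Speed = 10 m / time, so 300 s is 10/300 = 0.033 m/s. The later speeds are assumed.

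| Day 90 speed (assumed) | Change if baseline is 300 s | Change if baseline is unscored or 9999 |
|---|---|---|
| 0.20 m/s (50 s) | +0.17 m/s | none |
| 0.40 m/s (25 s) | +0.37 m/s | none |
| 0.80 m/s (12.5 s) | +0.77 m/s | none |

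The Day 90 case mirrors this: a patient at 0.40 m/s at baseline who cannot be walked at Day 90 contributes -0.37 m/s or nothing.

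**4. Effect on precision**

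The test has no sample-size figure of its own, so the trial's serves as the frame. Section 9.2 (difference 0.5, SD 1, two-sided 5%, 80% power) reproduces: a two-sample t-test needs 63.77, hence 64 per arm, 128 in total, with power 80.1%. Suppose a share of baselines is lost from 128 and the true effect on gait speed is 0.5 SD. Both the share and the effect are assumptions.

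| Share lost | Evaluable N = 128 x (1 - share) | Power |
|---|---|---|
| 0% | 128 | 80% |
| 5% | 122 | 78% |
| 10% | 115 | 76% |
| 20% | 102 | 71% |
| 30% | 90 | 65% |

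**5. Effect on the mean difference**

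Suppose a share p cannot be walked at baseline, 60% (active) and 40% (sham) of them regain 0.40 m/s, and the rest stay at 300 s. Coded 300 s at baseline, they add p x (0.60 - 0.40) x (0.40 - 0.033) to the overall difference: 0.007, 0.015 and 0.022 m/s for p = 10%, 20% and 30%. Coded as missing, they add nothing. All these inputs are assumed.

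**The case against.** - **The form has specific rules and states its intent.** Needing two helpers, not advancing the leg, not taking a step and exceeding 5 minutes each lead to 300 s, and the reminder pairs inability to walk with 300 s. A careful rater could let the specific rule win. This stands as evidence of intent. It does not remove the clash between untested subjects receiving 300 s and the reminder's restriction to assessed subjects, and it does not cover a safety judgement outside those triggers.
- **A 9999 entry requires a reason.** Some miscoded entries could be queried. That helps, but it means reclassifying patients afterwards. A statistical analysis plan can say how 9999 is analysed; it does not tell the rater which code to enter.
- **mRS 4 does not mean untestable.** A reader might infer that eligibility makes these patients common. The documents do not support that. Assistance at grade 4 includes verbal instruction and supervision, the test allows one person's physical help, and a patient unable to walk even with help is described under grade 5, which is not eligible. Some may still enter, since grade 5 is framed as being bedridden and Section 2.3.2 expects wheelchair users. No frequency is given.
- **Baseline coding precedes randomization, and the trial is blinded.** A reader might infer that baseline miscoding biases the comparison. It should not differ systematically by arm; the cost is mainly precision. Day 90 is different, because loss there depends on the outcome. If the device improves gait, dropping more poor sham outcomes would understate the benefit.
- **It is not the only lower-limb measure.** SIS-16, the fifth secondary endpoint, covers lower-extremity function by patient report.

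**Conclusion.** The point holds as an internal contradiction in the current form. A patient not walked because of gait impairment can be recorded as 0.033 m/s or be missing, depending on which line the rater follows. There are two effective outcomes; reading the form as giving three goes too far, since an unscored test and 9999 both leave no value.

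The difference per patient is clear: +0.37 m/s or nothing at an assumed later speed of 0.40 m/s. The trial-level size is not known. A reader might assume that half of 150 subjects are mRS 4 and that 10 to 30% of those are unsafe with one helper, giving about 8 to 23 subjects (75 x 0.10 to 75 x 0.30). Neither fraction is in the protocol, so that range is illustration only, as are the power and mean-difference figures above.

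The conflict is worth correcting because the endpoint gates three others, the Day 90 loss can be informative, and an analysis rule alone cannot fully repair inconsistent entries. It does not touch the primary endpoint.

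**What to change.** Reconcile the three parts of the form so that one code applies to each situation, the same at baseline and Day 90, in line with the form's own intent:

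1. Record 300 seconds on both trials whenever the walk is not done because of inability to walk or gait-related unsafety. This includes needing two or more persons, needing help to advance the leg, and being judged unsafe under the form's rules.
2. Reserve 9999, with the reason, for causes unrelated to walking ability, such as no available course, a remote visit or refusal.
3. Under Test Administration, replace the instruction not to score with one not to test and to record 300 seconds.
4. In the closing reminder, remove the condition that 300 seconds applies only to subjects who were assessed.

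The cost is a short form correction, rater retraining and more values at the floor, especially at baseline. Values already entered as 9999 should be checked against their recorded reasons while the data are still blinded.

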In addition to the hospital's standard therapy regimen of 1-hour daily treatments, both study groups sat within the BQ device for the duration of each treatment session and received 10 minutes of upper extremity PT/OT during the treatment session. The only difference between the investigational and sham treatment was whether or not the investigational device generated an EMF. Due to the non-invasive nature of the treatment, as well as the physical characteristic of the EMF, there was no noticeable difference between experimental conditions, and both subjects and operators were truly blinded. No significant differences between the baseline characteristics of the treatment and sham groups were identified.

The first four subjects were considered run-in subjects and were assigned directly to the treatment group. Due to early termination of the study, the expectation for meaningful outcomes beyond mere positive trends was limited. Still, the significant results and positive trends obtained in multiple metrics presented below, establish an indication of the efficacy of the treatment under investigation in reducing global disability in the subacute phase of ischemic stroke.

In a dichotomous analysis, where the percentage of subjects to reach little to no disability (mRS of 0-1) was compared to the percentage of subjects who remain with disability after treatment, the rate of non-disabled outcome (mRS 0-1) at final visit was 77% in the treatment group, versus only 25% of the sham-group subjects ($P = 0.03$). Furthermore, improvement by 2 or more mRS points occurred in 92% of subjects in the treatment group, compared to only 25% of the sham-group subjects ($P = 0.003$). This was reflected in the shift analysis of mRS scores in treated versus control subjects ([Figure 2](#)). While the results for the sham group are comparable to other sham data from similar longitudinal studies, the treatment group substantially outperformed investigational devices from other studies, as will be further presented below.

[figure not shown]

Figure 2. BQ3 study – shift analysis of mRS scores

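### The ALDS 1 form has no NA box, although the ALDS scoring rule requires NA for activities not attempted since the stroke and ALDS 2 to 5 provide it

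*Protocol*

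**What the plan says.** The ALDS is a tertiary/exploratory endpoint at Day 90 (Protocol section 3). Section 9.4.9 compares it between groups by analysis of variance. The forms are in Appendix 1 (section 12.1), and the Day 90 mRS decides which form is used.

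- **Scoring rule.** When the patient says that an item does not apply because he or she "has never attempted the activity in the question after stroke, then mark the 'NA' box". No form is exempted.
- **Same paragraph, first sentence.** "There are two response options which are 'Yes' and 'No".
- **Form for mRS 0 and 1.** "ALDS 1 : Assessment for Patient with Rankin Score 0 or Rankin Score 1". As extracted, the header and all 15 rows have two boxes, Yes and No.
- **Form for mRS 2.** "ALDS 2 : Assessment for Patient with Rankin Score 2". It has three boxes per row: Yes, No and NA. ALDS 3, 4 and 5 have the same three.
- **Second route to ALDS 1.** A patient at mRS 2 whose ALDS 2 answers are all Yes or NA must "proceed to ALDS 1 and assess all the *unique* questions in ALDS 1 that were not in ALDS 2".

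**The concern.** The instruction and the form do not fit together. A rater who follows the rule on ALDS 1 has no box to mark, and a rater who fills in only the printed boxes cannot follow the rule.

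The gap sits on one level of the scale. The form is chosen by Day 90 mRS, the visit and measure of the primary endpoint, so the recording of an unattempted activity depends on how well the patient has recovered. If the device works, more active than sham patients would be expected on ALDS 1, and the inconsistency would then be spread unevenly between the arms. What is at stake is the consistency of the endpoint that the protocol describes as the granular measure of disability. No other endpoint is involved.

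**Working it through.** **1. The forms side by side.** The protocol gives no figure on this point to reproduce. The check is a comparison of the text.

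| Form | Day 90 mRS | Response boxes |
|---|---|---|
| ALDS 1 | 0 or 1 | Yes, No |
| ALDS 2 | 2 | Yes, No, NA |
| ALDS 3 | 3 | Yes, No, NA |
| ALDS 4 | 4 | Yes, No, NA |
| ALDS 5 | 5 | Yes, No, NA |

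**2. Overlap of ALDS 1 and ALDS 2.** Matching the item lists gives 13 shared items out of 15. ALDS 1 alone asks about walking up a hill and a short walk. ALDS 2 alone asks about shopping for clothes and preparing breakfast or lunch. For 13 activities, then, the same unattempted task has a valid box at mRS 2 and none at mRS 0 or 1. A patient at mRS 2 who is sent on to ALDS 1 meets the gap only on the two items unique to that form.

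**3. Direction of a possible effect (illustration only).** These inputs are assumptions, not in the protocol: a simple percent-Yes score, Yes rate p = 0.9 among attempted items, share u of ALDS 1 items unattempted from 1/15 to 0.20, and NA items dropped from the score where NA is available. The shares at mRS 0 or 1 are a for active and s for sham. One pair comes from the pilot (section 2.2.2): "the rate of non-disabled outcome (mRS 0-1) at final visit was 77% in the treatment group, versus only 25% of the sham-group subjects". A milder pair, 40% against 25%, is assumed.

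Shift in the active-minus-sham difference, in points of 100, relative to dropping the items:

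- unattempted marked No: −100 × (a − s) × p × u
- unattempted marked Yes: +100 × (a − s) × (1 − p) × u
- left blank and dropped: 0

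| a vs s | u | Marked No | Marked Yes |
|---|---|---|---|
| 77% vs 25% | 1/15 | −100 × 0.52 × 0.9/15 = −3.1 | +0.3 |
| 77% vs 25% | 0.20 | −100 × 0.52 × 0.9 × 0.20 = −9.4 | +1.0 |
| 40% vs 25% | 1/15 | −100 × 0.15 × 0.9/15 = −0.9 | +0.1 |
| 40% vs 25% | 0.20 | −100 × 0.15 × 0.9 × 0.20 = −2.7 | +0.3 |
| equal shares | any | 0 | 0 |

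**4. Mixed marking.** If a fraction f of the unattempted items that receive a mark are marked No and the rest Yes, their mean score is 1 − f, against p for attempted items. With a > s, the net shift is against the device when f > 1 − p. That is f above 10% at p = 0.9 and above 30% at p = 0.7.

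**The case against.** **The table may have lost a column.** The text was read from PDF, and a lost column would vanish from the header and every row together. This cannot be excluded without the source page. It is unlikely, because the two-box grid is consistent from header to last row and the other four forms kept their third box. The check should come first.

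**A reader might infer that patients are forced to No and that the comparison is pulled toward no effect.** The document does not support that. No sentence tells the rater to mark No. The form refers the rater to the instruction sheets, which say NA, so a rater may write NA in or leave the row blank. Because the items ask what the patient can do, Yes is also possible. A patient rated mRS 0 or 1 on the RFA-A has just been recorded as not needing help with chores, travel or shopping. On the other side, the form asks for all questions to be assessed, and sections 10.1.8 and 10.1.9.1 have missing data queried, so a blank may come back to a rater who has two printed options. No is plausible, but it is not prescribed.

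**A reader might also infer that a patient with the better mRS gets the worse ALDS score.** That fails for the same reason. It also depends on how NA is scored, which the protocol does not state and may leave to the SAP.

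**The pilot rates exaggerate the scale.** They come from 13 and 8 patients, and section 9.2 sizes this trial on about 40% of the pilot difference. This objection stands.

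**Conclusion.** The mismatch holds: as extracted, ALDS 1 lacks the NA box that the scoring rule requires and that ALDS 2 to 5 carry, and the rule itself sits beside a statement that there are only two options. Unattempted activities have no valid response on the form for mRS 0 and 1, so their recording differs by Day 90 mRS.

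Attenuation of the ALDS comparison is conditional. It needs unattempted items to be marked No often enough and scored as failures, and more active than sham patients at mRS 0 or 1. Under the assumptions above the shift runs from −9.4 to +1.0 points of 100, and it is zero if the items are left blank and dropped or if the arms have equal shares at mRS 0 or 1. That range illustrates direction and does not estimate size, since the real ALDS is a calibrated item bank and not a percent-Yes score.

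The severity is minor. The ALDS is exploratory and outside the testing hierarchy of section 9.4.1, and the interim decision rules in section 9.4.6 do not use it.

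**What to change.** 1. Compare the ALDS 1 page with the source form. If the NA column is there, only the wording in step 4 needs correction.
2. If it is missing, add an NA box to all 15 ALDS 1 items on paper, and in the eCRF if it is absent there too (the eCRF is not shown).
3. Treat NA on ALDS 1 in the same way as on ALDS 2 to 5.
4. Reword the scoring paragraph in Appendix 1 so that the number of response options agrees with the NA rule.
5. If completed ALDS 1 forms are queried, do so before unblinding and ask about every answer: Yes, No and blank. Querying only No and blank answers would be a one-sided correction. It could only raise ALDS 1 scores, and would favour whichever arm has more patients at mRS 0 or 1.

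The cost is one column on one form, possibly one eCRF change, one corrected sentence and, if chosen, a short query round. No visits or patients are added, and no other analysis changes.
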